7.2.4.2. Rebound and SELENA SLEDAI Scores

Missing data will be imputed using the principle of Last Observation Carried Forward (LOCF). For the TH group, LOCF will not be applied across the TH and RS phases. If an individual SS item data is missing at the first timepoint in the RS phase, the item will be considered not present.

7.2.4.3. Changes in Corticosteroid Use

7.2.4.3.1. Number of days of daily prednisone dose ≥7.5 mg/day and/or increased by 25%

The Dropout (DO)/Prohibited Medication (PM)=Non-responder (NR) imputation will be applied. If a subject withdraws from the study and/or receives a protocol-prohibited medication, the subject will be considered to have met this endpoint criteria (i.e, dose \geq 7.5 mg/day and/or increased by 25%) after the date of dropout or the date that the medication is started, whichever comes first, up until the visit date, and for those days in intervals for subsequent attended visits. Before this date, the evaluated endpoint will be assessed using available data.

7.2.4.3.2. Number of days of daily prednisone dose ≤7.5 mg/day and/or decreased by 25%

The Dropout (DO)/Prohibited Medication (PM)=Non-responder (NR) imputation will be applied. If a subject withdraws from the study and/or receives a protocol-prohibited medication, the subject will be considered a non-responder for this endpoint criteria (i.e., dose >7.5 mg/day and/or did not decreased by 25%) after the date of dropout or the date that the medication is started, whichever comes first, and for those days in intervals for subsequent attended visits. Before this date, the evaluated endpoint will be assessed using available data.

7.2.5. Statistical Analyses / Methods

Details of the planned displays are provided in Appendix 11: List of Data Displays and will be based on GSK data standards and statistical principles.

Unless otherwise specified, endpoints / variables defined in Section 7.2.1 will be summarised using descriptive statistics, graphically presented (where appropriate) and listed.

7.3. Exploratory Efficacy Analyses

7.3.1. Endpoint / Variables

7.3.1.1. Physician Global Assessment (PGA)

The change from baseline in PGA score will be assessed at each visit in the 52-week treatment phase. See Section. 13.6.3 for additional details on the instrument.

7.3.1.2. SLICC/SDI

The change from baseline in SLICC/SDI score will be assessed at each visit in the 52-week treatment phase.

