3. INVESTIGATIONAL PLAN

3.1. Study Design

A phase IIIB, multi-centre, open-label, non-randomized, efficacy and safety study (including potential rebound) of:

- the effect of temporary discontinuation of belimumab 10 mg/kg therapy for 24 weeks and reintroduction of belimumab 10 mg/kg therapy for 28 weeks plus standard of care (referred to as 'treatment holiday') in subjects with low SLE disease activity (Figure 1).
- rebound phenomenon in subjects who have discontinued belimumab therapy (Figure 1).

Subjects will be recruited from 3 open-label continuation studies of belimumab in SLE. See Appendix 11.7 for recruitment from the open-label (OL) period BEL113750 for China subjects. This study will comprise 3 distinct groups of subjects as outlined below:

- Treatment Holiday group: This group will be used to assess the effect of temporary discontinuation (including rebound phenomenon) and re-introduction of belimumab 10 mg/kg therapy. These subjects will be recruited from the BEL114333 belimumab continuation study in subjects with SLE. Subjects will have been treated with belimumab for at least 6 months and have a SELENA SLEDAI score ≤3 and complement (C3 and C4) levels at or above the central laboratory lower limit of normal. The target enrolment for this group is at least 10 subjects.
- Treatment Control group: This group will serve as a control to the treatment holiday group. These subjects will be recruited from the BEL114333 belimumab continuation study in subjects with SLE. Subjects will have been treated with belimumab for at least 6 months and have a SELENA SLEDAI score ≤3 and complement (C3 and C4) levels at or above the central laboratory lower limit of normal but will continue their current treatment with belimumab 10 mg/kg. The target enrolment for this group is at least 26 subjects.
- Long-term Discontinuation group: This group will also be used to assess rebound phenomenon in SLE subjects who have discontinued therapy with belimumab 10 mg/kg and are expected to remain off belimumab therapy for at least 12 months but remain on standard of care therapy. These subjects will be recruited from 3

CONFIDENTIAL

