Physical Examination		Х															
Inclusion/Exclusion		Х															
Efficacy Assessments																	
DAS: SS, SLE Flare Index, PGA ⁵	X 1	Х	Х	Х	Х	Х	Х	Х	Х	Х	Х	Х	Х	Х	х		
SLICC/ACR Damage Index		Х						Х							Х		
Safety Assessments			•	•								•		•	•		
Vital Signs 6		Х	Х	Х	Х	Х	Х	Х	Х	Х	Х	Х	Х	Х	Х	Х	
Weight, height ^{6, 7}		Х	Х	Х	Х	Х	Х	Х	Х	Х	Х	Х	Х	Х	Х		
Symptom-driven Physical Exam		Х	Х	Х	Х	Х	Х	Х	Х	Х	Х	Х	Х	Х	Х	Х	
Record Concurrent Medications		Х	Х	Х	Х	Х	Х	Х	Х	Х	Х	Х	Х	Х	Х	Х	
Adverse Events		Х	Х	Х	Х	Х	Х	Х	Х	Х	Х	Х	Х	Х	Х	Х	
Laboratory Assessments			•	•								•		•	•		
Haematology & Modified Chem 20 (non-fasting) ⁶	Х	Х	Х	Х	Х	Х	Х	Х	Х	Х	Х	Х	Х	Х	Х	Х	
Urinalysis	Х	Х	Х	Х	Х	Х	Х	Х	Х	Х	Х	Х	Х	Х	Х	Х	
Spot urine (protein to creatinine ratio) ⁸	Х	Х	Х	Х	Х	Х	Х	Х	Х	Х	Х	Х	Х	Х	Х		
Pregnancy Test 6, 9	U	U	U	U	U	U	U	U	U	U	U	U	U	U	U	U	
Pharmacogenetic Sampling ¹⁰		Х															
aCL Autoantibody		Х													Х		
C3/C4	Х	Х	Х	Х	Х	Х	Х	Х	Х	Х	Х	Х	Х	Х	Х		

2012N154810_06

CONFIDENTIAL

2018N381035_00

BEL116027

	Screen		Treatment Holiday Study												Follow-up		
Visit	1	2	3	4	5	6	7	8	9	10	11	12	13	14	15		
Study Day	Up to -30 ¹	0 ²	28 ±7d	56 ±7d	84 ±7d	112 ±7d	140± 7d	168 ±7d	196± 7d	224 ±7d	252 ±7d	280± 7d	308 ±7d	336 ±7d	364 ±7d or Exit	16-wk ±7d ³	6 mo ±7d
Study Week		0	4	8	12	16	20	24	28	32	36	40	44	48	52		
Anti-dsDNA Autoantibodies	Х	Х	Х	Х	Х	Х	Х	Х	Х	Х	Х	Х	Х	Х	Х		
ANA Autoantibodies		Х						Х							Х		
IgG, IgA & IgM ¹¹		Х		Х		Х		Х		Х		Х		Х	Х		
PT/ PTT		Х															
Exploratory Lab Assessments	3																
Pharmacokinetic Sampling ¹²		Х		Х		Х		X 12		Х					X 12		
Immunogenicity ^{6, 13}		Х			Х		X 13	Х			Х				Х	Х	X 13
BLyS Protein 14						Х		Х		Х							
B cell Markers ¹⁵		Х		Х		Х		Х		Х		Х			Х		X
Investigational Product (IP)																	
IP Administration ¹⁶		Х	Х	Х	Х	Х	Х	Х	Х	Х	Х	Х	Х	Х	X		

DAS = disease activity scales; SS = SELENA SLEDAI; SLE = systemic Lupus Erythematosus; PGA = Physician's Global Assessment; SLICC/ACR = Systemic Lupus International Collaborating Clinics/American College of Rheumatology; ALT = alanine aminotransaminase; AST = aspartate aminotransaminase; PT/PTT = prothrombin time/partial thromboplastin time; BlyS = B Lymphocyte Stimulator; IP = investigational product; aCL = anticardiolipin

1. A screening visit of up to 30 days prior to the Day 0 visit will be scheduled for subjects in the treatment holiday and control groups for assessment of SELENA SLEDAI score to assess eligibility.

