6.3.2. SLICC/ACR Damage Index

The Systemic Lupus International Collaborative Clinics/American College of Rheumatology (SLICC/ACR) Damage Index is a validated instrument developed to assess the accumulated damage in patients with SLE, resulting from either the disease process or its sequelae. It can identify changes in damage seen in patients with both active and inactive disease and records damage occurring in patients with SLE regardless of its cause [Gladman, 1996]. The index is a predictor of severe outcome and an indicator of morbidity in different ethnic groups [Stoll, 1996]. SLICC/ACR Damage Index was designed to be useful both as a descriptor for patient populations included in studies, and as an outcome measure for therapeutic trials and studies of prognosis [Gladman, 1996].

The SLICC/ACR Damage Index consists of 39 items in 12 different organ systems. For a feature to represent damage, it must be present for at least 6 months, to enable discrimination between active inflammation and tissue damage [Gladman, 1996]

Scoring is usually 0 or 1, although in 6 items, a score of 2 can be given if there is a repeat episode more than 6 months apart. The exception is end-stage renal disease, which scores 3.

A copy of the SLICC/ACR Damage Index is provided in Appendix 2.

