7. EFFICACY ANALYSES

For all efficacy analyses, results for the TH group will be presented for the treatment holiday (TH) and re-start (RS) phases separately.

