7.3.4.2. SLICC/SDI

Missing data due to study withdrawal will be imputed using LOCF. For the TH group, LOCF will not be applied across the TH and RS phases.

The SLICC/ACR Damage Index increases over time. Once a subject meets the criteria for positive scoring of an item, that item should always be marked as present, even if the subject subsequently recovered.

In the event the SLICC/ACR Damage Index is scored inconsistently (a decrease relative to previous items has occurred) and the data are unable to be queried and/or corrected, a worst observation carried forward (WOCF) approach will be used at the item level for the SLICC/ACR Damage Index questions. These WOCF values will then be used to calculate the total score which will be the value summarized and displayed for reporting.

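### New SLICC damage that starts in the 24-week holiday is too young to score at Week 24, so the SAP's phase split will normally show it under Re-start, and the carry-forward rule treats the holiday group differently at Week 52

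*SAP*

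**What the plan says.** Protocol Section 6.3.2 sets the persistence rule: "For a feature to represent damage, it must be present for at least 6 months". It also allows six items a higher score: "a score of 2 can be given if there is a repeat episode more than 6 months apart". The "SLICC/ACR Damage Index" row of the Year 1 Time and Events table (Protocol Section 6, Table 2) has three marks only: Day 0, Week 24 (Day 168 ±7) and Week 52 or Exit (Day 364 ±7). SAP 7.3.1.2 nevertheless states: "The change from baseline in SLICC/SDI score will be assessed at each visit in the 52-week treatment phase".

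The design under study is "temporary discontinuation of belimumab 10 mg/kg therapy for 24 weeks" followed by re-introduction (Protocol 3.1). For all efficacy analyses, SAP Section 7 says that "results for the TH group will be presented for the treatment holiday (TH) and re-start (RS) phases separately". SAP 13.4.1.1 lists SLICC among the endpoints divided into Holiday and Re-start phases. SAP 13.4.1 assigns an assessment made on a cut-point date to the earlier phase. Week 24 SLICC is therefore a holiday value and Week 52 SLICC a re-start value. SAP 5.3.1 sets the SLICC baseline at Day 0 of this study and does not reset it at re-start.

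On missing data, SAP 7.3.4.2 carries the last score forward after withdrawal (13.7.2 adds prohibited medication) but limits this: "For the TH group, LOCF will not be applied across the TH and RS phases". The same section says: "Once a subject meets the criteria for positive scoring of an item, that item should always be marked as present".

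**The concern.** The holiday is shorter than the time a feature must persist before it counts. A display divided at Week 24 therefore sorts damage by when it became scorable, while its labels suggest when it arose. The study exists to characterise treatment holidays. A reader of the phase columns could take a low Week 24 change as reassurance about the holiday, or take new Week 52 points as damage that arose after belimumab was re-started. Neither reading follows from how the index is scored.

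The missing-data rule raises a second, separate issue. For an index whose items stay scored once present, a holiday subject with no re-start score has no Week 52 value. A control or long-term discontinuation subject who withdraws after Week 24 keeps one. The Week 52 comparison would then rest on differently selected groups.

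**Working it through.** The plan gives no figure to reproduce here; the check is day arithmetic.

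**Inputs.** Six months is 181 to 184 calendar days; 183 is used, with a range shown. Week 24 is Day 168, or Day 175 at the late edge of its window. Week 52 is Day 364, with a window of Day 357 to Day 371. All visit days are from Protocol Table 2.

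**Formula.** Latest onset scorable at a visit = visit day − length of 6 months.

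| 6 months taken as | Week 24 nominal (168 − m) | Week 24 late (175 − m) | Week 52 nominal (364 − m) |
|---|---|---|---|
| 180 days | Day −12 | Day −5 | Day 184 |
| 181 days | Day −13 | Day −6 | Day 183 |
| 183 days | Day −15 | Day −8 | Day 181 |
| 184 days | Day −16 | Day −9 | Day 180 |
| 168 days (extreme reading) | Day 0 | Day 7 | Day 196 |

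**Week 24.** For any length from 180 to 184 days, the latest scorable onset falls before Day 0, even at a late visit. No new holiday-onset feature qualifies. Only reading 6 months as exactly 24 weeks lets in onset on Day 0, or up to Day 7 at a late visit.

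**Week 52.** A feature starting on the last holiday day is 364 − 168 = 196 days old at nominal visits. At the worst combination of windows it is 357 − 175 = 182 days old. Essentially all persisting holiday-onset damage is scorable by then.

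**Where new points between Week 24 and Week 52 come from.** With 183 days, eligible onset runs from 168 − 183 = Day −15 to 364 − 183 = Day 181, which is 196 days:

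- before Day 0: 15 days, 15/196 = about 8%
- holiday: 168 days, 168/196 = about 86%
- re-start: 181 − 168 = 13 days, 13/196 = about 7%

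The re-start period itself lasts 364 − 168 = 196 days, so only about 7% of it can produce new damage scorable by Week 52.

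**Where new points between Day 0 and Week 24 come from.** Eligible onset runs from about Day −183 to Day −15, all before the holiday.

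**Carry-forward.** Week 52 or an Exit visit is the only scheduled SLICC assessment in the re-start phase. SAP 13.4.1 gives subjects who re-start before Week 24 no re-start phase, and their next scheduled SLICC is Week 48 of the additional-years table (Protocol Table 3). Escapers and holiday-phase withdrawals therefore have no Week 52 value. With 12 holiday subjects enrolled (SAP 2.3), each such subject is 1/12 = about 8% of the group. The documents do not say how many there are; three, for illustration, would be 25%.

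**The case against.** A reader might infer that the split reverses attribution, that the holiday must look free of damage, and that holiday-onset damage can appear only at Week 52. The documents do not support any of these.

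- **The Week 52 change is cumulative.** With baseline fixed at Day 0, the Week 52 value for the holiday group already includes the holiday. A column label does not turn it into a re-start-only change, and the Week 52 comparison with control keeps the holiday damage among subjects with a score.
- **Week 24 is not an assured zero.** Features that began before Day 0 can reach 6 months during the holiday. A repeat episode in one of six items may also raise the score, since the protocol does not say that the repeat must itself persist.
- **Exit visits count.** An Exit assessment after about Day 183 can record holiday-onset damage.
- **The limit at Week 24 is shared.** Control and long-term discontinuation subjects face the same rule, so a Week 24 comparison is uninformative about new onset, not tilted towards the holiday.

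These points stand. They narrow the problem to labelling and interpretation.

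On carry-forward, the objection is that a Week 24 score cannot contain new holiday-onset damage, so carrying it to Week 52 may hide what is sought. In addition, the permanence sentence in SAP 7.3.4.2 leads into a rule for inconsistent scoring, not for unobserved visits. Both are fair. They argue for calling a carried score a lower bound. They do not justify carrying scores for two groups and not the third.

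The instrument and the table shells are not in the public documents, so item-level rules and the exact layout of Table 3.3 cannot be checked.

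**Conclusion.** The point holds as a mismatch between the phase labels and the scoring rule. New damage starting in the holiday cannot be scored at an in-window Week 24 visit. It will normally first appear at Week 52, or at an Exit visit after about Day 183, and the SAP files it under Re-start. The shift is about one phase: roughly 86% of eligible onset days for new Week 24 to Week 52 points lie in the holiday and 7% in re-start. Those percentages count days; reading them as shares of damage also assumes a roughly constant onset rate, which the documents do not give. The result also rests on the protocol's 6-month sentence applying to every new item.

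The unequal carry-forward is a separate defect, confined to holiday subjects with no re-start score.

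The consequence is modest. SLICC is an exploratory endpoint, summarised descriptively, with 12 holiday subjects; no primary result depends on it and completers' data are intact. It is still worth correcting, because damage after a treatment holiday is a result that readers of this study will look for.

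**What to change.** - In SAP Section 7, exempt SLICC from the phase split. Present the Day 0 to Week 52 change as the SLICC summary for all three groups, and read holiday versus control at Week 52.
- Footnote Week 24 in Table 3.3 as unable to include new damage with onset after Day 0.
- In SAP 7.3.4.2 and 13.7.2, apply the same carry-forward of already scored items to Week 52 in all three groups, and name escapers explicitly, since they have not withdrawn from the study. Describe the result as a lower bound, give the number of imputed holiday-group values, and show an observed-only summary alongside.
- In SAP 7.3.1.2, name the scheduled SLICC visits.

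The cost is SAP wording, one table note and one extra summary, with no new data. The downside is that a carried Week 24 score cannot include new holiday-onset damage and may understate it, which is why the observed-only summary is needed.

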7.3.1.3. Renal Flare

The time to the first renal flare over 52 weeks will be estimated for the treatment groups using the product-limit method. See Section 13.6.3 for additional details.

7.3.2. Summary Measure

7.3.2.1. Physician Global Assessment (PGA) and SLICC/SDI

These endpoints will be analyzed using summary statistics.

7.3.2.2. Renal Flares

Only post-baseline renal flares will be considered in these analyses. Renal flares (not subjects) occurring on the Day 0 visit date should be removed from the analysis set prior to determining the first renal flare.

Data observed at or prior to the baseline visit (see Section 5.3.1) will not be included in this analysis.

Time to first renal flare is defined as the number of days from baseline date (see Section 5.3.1) to the date the subject has a renal flare (event date – baseline visit date + 1).

7.3.3. Population of Interest

The analyses for all exploratory endpoints will be based on the ITT population.

For renal flares, the analysis will be repeated for subjects with baseline proteinuria proteinuria >0.5g/24hr equivalent.

7.3.4. Strategy for Intercurrent (Post-Randomization) Events

7.3.4.1. Physician Global Assessment (PGA)

Missing data will be imputed using LOCF. For the TH group, LOCF will not be applied across the TH and RS phases.

7.3.4.2. SLICC/SDI

Missing data due to study withdrawal will be imputed using LOCF. For the TH group, LOCF will not be applied across the TH and RS phases.

The SLICC/ACR Damage Index increases over time. Once a subject meets the criteria for positive scoring of an item, that item should always be marked as present, even if the subject subsequently recovered.

In the event the SLICC/ACR Damage Index is scored inconsistently (a decrease relative to previous items has occurred) and the data are unable to be queried and/or corrected, a worst observation carried forward (WOCF) approach will be used at the item level for the SLICC/ACR Damage Index questions. These WOCF values will then be used to calculate the total score which will be the value summarized and displayed for reporting.

7.3.4.3. Renal Flare

The disposition of subjects as it relates to intercurrent events is defined as follows:

Subject Disposition	Event Met	Event Date [2]			
Subject has a renal flare or takes a prohibited medication					
Subject has a renal flare [1]	Yes	Date of first renal flare			
Subject takes a prohibited	Yes	Date of prohibited medication			
medication [1]					
Subject does not have a renal flare and did not take a prohibited medication					
Subject withdraws	No	Censored at last flare			
		assessment date			
Subject dies	No	Censored at date of death			
Subject completes	No	Censored at the Week 52			
		study visit			

[1] If a subject has a renal flare and takes a prohibited medication, the event date is the earliest of the first renal flare date and takes a prohibited medication date.

[2] If a subject meets multiple criteria, then the event date is the earliest date.

7.3.5. Statistical Analyses / Methods

Details of the planned displays are provided in Appendix 11: List of Data Displays and will be based on GSK data standards and statistical principles.

Unless otherwise specified, endpoints / variables defined in Section 7.3.1 will be summarised using descriptive statistics, graphically presented (where appropriate) and listed.

7.4. Efficacy Data for Maintenance Phase Subject Profile

Flare data will be listed on the subject profile.

8. SAFETY ANALYSES

The safety analyses will be based on the ITT population, unless otherwise specified.

8.1. Adverse Events Analyses

Adverse events analyses including the analysis of adverse events (AEs), serious adverse events (SAEs), and other significant AEs will be based on GSK Core Data Standards. The details of the planned displays are provided in Appendix 11: List of Data Displays.

Adverse events will be coded to the current MedDRA dictionary version available at the time of reporting.

Only treatment emergent AEs will be summarized (see Section 13.4.1). Any AEs that were ongoing in the upon entry into this will be listed and flagged with a footnote

An overall summary of AEs will be presented showing the number (%) of subjects with at least one of the following: AE, related AE, SAE, severe AE, SAE and/or severe AE, AE resulting in study treatment discontinuation, and deaths.

The number of events and the number (%) of subjects experiencing an AE by SOC, SOC and PT, and PT will be summarized for each of the AE categories below.

- All
- Serious
- Severe
- Study agent Related
- Resulting in discontinuation of study treatment

The data will be sorted by overall decreasing frequency of the SOC, by overall decreasing frequency of the SOC and then decreasing frequency of PT within the SOC, and by overall decreasing frequency of the PT, as applicable. Only SOCs with observed AE PTs will be presented. If the frequency for any two or more adverse events is equal, the events will be presented in alphabetical order by SOC/PT as applicable.

Summaries of AEs frequency by SOC and severity will also be provided. For these displays, the number and percentage of subjects will be summarized as mild, moderate, or severe based on the maximum severity observed across all PTs within the SOC for a given subject.

The hierarchical relationship between MedDRA SOCs, PTs, and verbatim text will be displayed in a table for all AEs.

A listing of which subjects reported each AE will be produced. AEs will be grouped and sorted by SOC and PT. A listing of Infusion Related Systemic Reactions will be produced.

